- c. **Statistical Analysis**: The Fisher Exact test will be use to compare 28day mortality in the two groups. Statistical significance will be determined according to the interim analyses procedures describe below. If adjustment for pre-defined confounders is needed, we will use the above-defined method for categorical, binary variables.
- d. **Interim analyses:** We planned 5 analyses (4 interim, 1 final), equally spaced, using the O'Brien-Fleming method to calculate two-sided boundaries, assuming a 95% confidence and 80% power. All patients entered in each interim analyses will have complete data on 28-day mortality (i.e., the analyses will be conducted only once the 28-day observation period for all survivors have been completed).
- e. **Sample Size and Power:** This is a Phase 2 trial and is powered to detect large (17 to 19 percent-point) differences in mortality between the two groups.

Primary endpoint power calculations: 28-day mortality

Assumptions: 80% power, 95% confidence, 2-tailed test, P2=mortality in control group, P1=mortality in experimental group; 3 equally spaced data analyses, as determined by number of patients enrolled (2 interim when 1/3 and 2/3 of the predicted sample or 20 and 40 patients were enrolled, and a final when 60 to 75 patients were enrolled), using the O'Brien-Fleming method; control group 30-day mortality of 26% (based on control arm of ROC HS trial⁶⁷) and three attrition rates (0, 10%, 20%)

	Power	N1	N2	Alpha	Beta	P1	P2	Difference	Attrition Rate
	0.800000	60	60	0.050000	0.200000	0.07	0.26	0.19	20%
	0.800000	68	68	0.050000	0.200000	0.08	0.26	0.18	10%
L	0.800000	75	75	0.050000	0.200000	0.09	0.26	0.17	0%

Sample size of 60 and 60 achieves 80% power to detect a difference of 0.19 between the group proportions at a significance level (alpha) of 0.05 using a two-sided test. These results assume that 3 sequential tests are made using the O'Brien-Fleming spending function to determine the test boundaries, as seen below.

Boundaries (Bndry) for data looks Details when Spending = O'Brien-Fleming, N1 = 60, N2 =60, P1 = 0.07, P2 = 0.26 Lower Upper Nominal Inc Total Inc Total

^{*} Although the hypothesis is worded as "higher", all tests will be two-tailed to control for differences in either direction (higher or lower than the other group).

Look	Bndry	Bndry	Alpha	Alpha	Alpha	Power	Power
1	-3.71030	3.71030	0.000207	0.000207	0.000207	0.018650	0.018650
2	-2.51142	2.51142	0.012025	0.011890	0.012097	0.398801	0.417451

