3	-1.99302	1.99302	0.046259	0.037903	0.050000	0.382549	0.800000
Details whe	en Spending = C)'Brien-Flem	ning, N1 = 68	, N2 =68, P1	= 0.08, P2 =	0.26	
	Lower	Upper	Nominal	Inc	Total	Inc	Total
Look	Bndry	Bndry	Alpha	Alpha	Alpha	Power	Power
1	-3.71030	3.71030	0.000207	0.000207	0.000207	0.018650	0.018650
2	-2.51142	2.51142	0.012025	0.011890	0.012097	0.398801	0.417451
3	-1.99302	1.99302	0.046259	0.037903	0.050000	0.382549	0.800000
Details whe	en Spending = C)'Brien-Flem	ning, N1 = 75	, N2 =75, P1	= 0.09, P2 =	0.26	
	Lower	Upper	Nominal	Inc	Total	Inc	Total
Look	Bndry	Bndry	Alpha	Alpha	Alpha	Power	Power
1	-3.71030	3.71030	0.000207	0.000207	0.000207	0.018650	0.018650
2	-2.51142	2.51142	0.012025	0.011890	0.012097	0.398801	0.417451
3	-1.99302	1.99302	0.046259	0.037903	0.050000	0.382549	0.800000

Addendum Nov 16, 2016

At the second interim analyses, we had enrolled 100 patients (2/3 of the 150 total sample size), of whom 88 (12% attrition rate) patients were eligible for analysis (please, see Interim Analyses report for details). This attrition rate was similar to the lowest anticipated attrition rate (see first table above). Yet we noticed several important differences regarding the assumptions used to estimate the sample size. In brief, the cohort enrolled based on the entry criteria (field systolic blood pressure, SBP<70mmHg or SBP <90mmHg AND heart rate>108bpm) was less severely injured than anticipated (as measured by base deficit, INR and TEG G) and had lower mortality than anticipated.

Variable	Anticipated (sample size/power analyses assumptions)	COMBAT group A	COMBAT group B
INR	1.47	1.32	1.38
INR>1.5	24% to 36% *	18%	16%
Base deficit (mEq/L)	5.15	11.2	9.2
TEG G dynes/cm ²	4.9	7.3	7.5
Mortality	26%	12%	13%

* {MacLeod, 2003 #1415;Maegele, 2007 #905;Niles, 2008 #4410}

In addition, a slightly lower proportion of patients required transfusions (55% of group A, 61% of group B) compared to our anticipated proportion based on trauma registry data encompassing the period of January 2009-December 2011 (3 years) and excluding patients who died within 10 minutes of arriving at ED (64%).

Although we enrolled a cohort with less physiologic and coagulation derangement than anticipated, which decreased our statistical power to detect differences in the primary and secondary outcomes, we detected some promising trends, as follows:

[figure not shown]

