There are several explanations for the differences in the expected and observed values. First, for the most common injury mechanisms, the case-fatality rate is decreasing in our trauma center ([name] et al. JAMA, 2016). Second, the wide use of TEG-guided hemostatic resuscitation in our institution has been associated with a dramatic decrease in post-injury mortality (Gonzalez, Ann Surg, 2016). In addition, our findings are not isolated. A recent multicenter RCT (Connelly et al., JAMA Surgery, 2016) also noted that the patients enrolled were less severely injured than anticipated based on previous experiences. Given the time required to establish such intense trials, usually one to two years, the assumptions used in the calculation of the sample size can understandably become outdated. This has prompted proposals of alternative designs for RCTs, such as adaptive and Bayesian RCTs as recently described by an NIH-funded workshop (Coffey et al. Clinical trials, 2012).

Based on the explanations above, we propose a continuation of the trial to increase sample size and make it adequate to detect differences in the proposed outcomes (mortality, admission acidosis and coagulation, hemorrhage as well as requirement for blood products), as follows:

Hypothesis for primary endpoint above: 28-day mortality will be significantly higher in control patients compared to experimental patients.

With 80% power, 95% confidence and assuming 12% mortality rate in the control group (based on the second interim analyses data), with 5 interim analyses (4 interim and 1 final, of which 3 already occurred), we will require 112 patients in each group (assuming the attrition rate observed in this RCT of 12%) to detect a difference of 10 percent points. This results in a total of 224 patients, which corresponds to an increase of 74 patients over the current sample size of 150 patients. See below the significance level for the 5 analyses.

Spending = O'Brien-Fleming, N1 = 112, N2 =112, P1 = 0.12, P2 = 0.02, Continuity Correction.

		Lower	Upper	Nominal	Inc	Total	Inc	Total
Look	Time	Bndry	Bndry	Alpha	Alpha	Alpha	Power	Power
1	0.20	-4.87688	4.87688	0.000	0.000	0.000	0.00015	0.000
2	0.40	-3.35695	3.35695	0.001	0.001	0.001	0.05885	0.059
3	0.60	-2.68026	2.68026	0.007	0.007	0.008	0.25750	0.317
4	0.80	-2.28979	2.28979	0.022	0.017	0.024	0.28890	0.605
5	1.00	-2.03100	2.03100	0.042	0.026	0.050	0.19460	0.800

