Secondary Endpoint 4: Admission acidosis. This is an endpoint for which there is ample evidence of a strong association of postinjury mortality and serious complications. ⁹¹⁻¹⁰⁰

a. Definition: Admission acidosis will be defined through base deficit (BD) or lactate levels upon ED arrival. The target time point is 30 minutes after ambulance arrival to injury scene. Our institution's average time from arrival of ambulance to scene till arrival in ED is 28 minutes. ⁸⁸ If both base deficit and lactate are obtained more than 60 minutes from arrival of ambulance to scene, they will not be used to define the endpoint.

- b. **Hypothesis 4.1:** Admission BD will be higher^{‡‡} among control patients compare to the experimental group patients.
- c. **Statistical test 4.1:** Linear regression will be used to compare the mean admission base deficit of the two groups. Statistical significance will be determined according to the interim analyses procedures describe below. If adjustment for pre-defined confounders is needed, we will use the above-defined method for continuous, normally distributed variables.
- d. **Interim analyses:** We planned 5 analyses (4 interim, 1 final), equally spaced, using the O'Brien-Fleming method to calculate two-sided boundaries, assuming a 95% confidence and 80% power.
- e. **Sample size and Power calculations:** This is a Phase 2 trial, powered to detect differences in this outcome as follows:

Power calculations: Admission Base Deficit

Assumptions 1: 80% power, 95% confidence, 2-tailed test, 3 equally spaced data analyses (2 interim, 1 final), using the O'Brien-Fleming method; control group mean admission BD=5.15 and standard deviation (SD) =5.1 (based on⁹²)

Power	N1	N2	Alpha	Beta	Mean 1	Mean 2	SD	Difference	Attrition Rate
0.800000	60	60	0.050000	0.200000	5.15	2.52	5.10	2.63	20%
0.800000	68	68	0.050000	0.200000	5.15	2.68	5.10	2.47	10%
0.800000	75	75	0.050000	0.200000	5.15	2.80	5.10	2.35	0

Sample sizes of 60 and 60 achieve 80% power to detect a difference of 2.63 between the two means, a clinically relevant difference, at a significance level (alpha) of 0.05 using a two-sided test. These results assume that 3 sequential tests are made using the O'Brien-Fleming spending function to determine the test boundaries.

Boundaries (Bndry) for data looks

	iury) ior uata i						
Details when S	pending = O'Br	ien-Fleming,	N1 = 60, N2 =	=60, S1 = 5.10,	S2 = 5.10, Di	ff = 2.63	
	Lower	Upper	Nominal	Inc	Total	Inc	Total

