Look	Bndry	Bndry	Alpha	Alpha	Alpha	Power	Power
1	-3.71030	3.71030	0.000207	0.000207	0.000207	0.018650	0.018650
2	-2.51142	2.51142	0.012025	0.011890	0.012097	0.398801	0.417451
3	-1.99302	1.99302	0.046259	0.037903	0.050000	0.382549	0.800000
Details when S	pending = O'Br	·ien-Fleming,	N1 = 68, N2 =	=68, S1 = 5.10,	S2 = 5.10, Di	ff = 2.47	
	Lower	Upper	Nominal	Inc	Total	Inc	Total
Look	Bndry	Bndry	Alpha	Alpha	Alpha	Power	Power
1	-3.71030	3.71030	0.000207	0.000207	0.000207	0.018650	0.018650
2	-2.51142	2.51142	0.012025	0.011890	0.012097	0.398801	0.417451
3	-1.99302	1.99302	0.046259	0.037903	0.050000	0.382549	0.800000
Details when S	pending = O'Br	ien-Fleming,	N1 = 75, N2 =	=75, S1 = 5.10,	S2 = 5.10, Di	ff = 2.35	
	Lower	Upper	Nominal	Inc	Total	Inc	Total
Look	Bndry	Bndry	Alpha	Alpha	Alpha	Power	Power
1	-3.71030	3.71030	0.000207	0.000207	0.000207	0.018650	0.018650
2	-2.51142	2.51142	0.012025	0.011890	0.012097	0.398801	0.417451
3	-1.99302	1.99302	0.046259	0.037903	0.050000	0.382549	0.800000

^{‡‡} Although the hypothesis is worded as "higher", all tests will be two-tailed to control for differences in either direction (higher or lower than the other group).

Addendum November 16, 2016

Based on the interim analyses, a proposed new sample size is: with 80% power, 95% confidence and assuming mean admission BD = 11 mEq/L with standard deviation of 6.3 in the control group (based on the second interim analyses data), with 5 interim analyses (4 interim and 1 final, of which 3 already occurred), we will require 112 patients in each group (assuming the attrition rate observed in this RCT of 12%) to detect a difference of 2mEq/L (from 11 to 9mEq/L) between the two mean BDs. This results in a total of 224, which corresponds to an increase of 74 patients over the current sample size of 150 patients.

- f. Hypothesis 4.2: Admission lactate will be higher^{§§} among control patients compare to the experimental group patients. Statistical test 3.2: Linear regression will be used to compare the mean admission lactate of the two groups. Statistical significance will be determined according to the interim analyses procedures describe below. If adjustment for pre-defined confounders is needed, we will use the above-defined method for continuous, normally distributed variables.
- g. **Interim analyses:** We planned 5 analyses (4 interim, 1 final), equally spaced, using the O'Brien-Fleming method to calculate two-sided boundaries, assuming a 95% confidence and 80% power.

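### The addendum's 112 per arm is both the number analysed and the number enrolled, so the stated 12% attrition was never applied; and base deficit has 65% power, not 80%, even with no losses

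*Combined protocol and SAP*

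**What the plan says.** Section IV.E.1.e, addendum of 16 November 2016, re-derives the sample size for 28-day mortality at 12% in the control group and a 10-point difference, with five O'Brien-Fleming analyses. It says "we will require 112 patients in each group (assuming the attrition rate observed in this RCT of 12" per cent). The power table below it is headed "N1 = 112, N2 =112, P1 = 0.12, P2 = 0.02, Continuity Correction" and ends at total power 0.800. The text then states: "This results in a total of 224 patients, which corresponds to an increase of 74 patients over the current sample size of 150 patients".

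The same addendum counts the 150 as enrolment and shows where the 12% comes from: "we had enrolled 100 patients (2/3 of the 150 total sample size), of whom 88 (12% attrition rate) patients were eligible for analysis".

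The attrition parenthesis, with 112 per group and 224 in total, appears eight times: mortality and Hypothesis 5 (TEG G) in IV.E, the composite in IV.F.1, INR and INR above 1.5 in IV.F.2, TEG G in IV.F.3, and base deficit and lactate in IV.F.4. Each carries an 80% power claim. For base deficit the claim is made "assuming mean admission BD = 11 mEq/L with standard deviation of 6.3 in the control group", "to detect a difference of 2mEq/L (from 11 to 9mEq/L) between the two mean BDs".

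The original design handled attrition differently. It considered "three attrition rates (0, 10%, 20" per cent) and lowered the table's N accordingly, to 75, 68 and 60 per arm.

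**The concern.** An attrition allowance separates two numbers: those enrolled and those analysed. Here 112 stands for both. It is the N at which the power program reports 80%, so it is the analysed number. It is also half of a total that the addendum places on the enrolment scale (150 plus 74). A reader is told that the extension is protected against the observed 12% loss when it is not.

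The 74-patient extension is justified by an 80% power claim for each endpoint, so those claims should be correct as printed. The base-deficit claim also appears too optimistic at 112 per arm whatever is assumed about losses.

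**Working it through.** **Inputs.** The five printed boundaries are 4.87688, 3.35695, 2.68026, 2.28979 and 2.03100 at information times 0.2 to 1.0 (IV.E.1.e addendum). Rates, differences and SDs come from the eight addendum paragraphs. The addendum gives SDs for the control group only. Equal SDs in both arms are assumed here, as in the original tables of IV.F.

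**1. Reproduce the addendum's table.** Numerical integration over the printed boundaries gives total alpha 0.0500. The incremental powers match the table (0.00015, 0.0588, 0.2575, 0.2889, 0.1946). The drift for 80% power is 2.836. With continuity correction at N = 112, 80% is reached when the experimental rate is 1.6-1.7%, which prints as 0.02. So 112 is the analysed number in that table.

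**2. Check the original convention.** The original three-look boundaries need a drift of 2.819. Detectable difference = 2.819 × SD × √(2/n). For base deficit (SD 5.1) at n = 75, 68 and 60 this gives 2.35, 2.47 and 2.63, as printed; compare "Sample sizes of 60 and 60 achieve 80% power to detect a difference of 2.63 between the two means". TEG G (SD 2.3) gives 1.06, 1.11 and 1.18, and lactate (SD 2) gives 0.92, 0.97 and 1.03, also as printed. The table's N was therefore the number left after attrition. The same method with 12% loss would have used 112 × 0.88 = 98.6 per arm.

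**3. Test whether 112 is already inflated from about 99.** For a continuous endpoint, analysed n per arm = 2 × (2.836 × SD / difference)².
- INR: 2 × (2.836 × 0.5 / 0.19)² = 111.4, which fits 112 analysed, not 99.
- TEG G: the detectable difference is 2.836 × 3 × √(2/112) = 1.14, printed as 1.1. At 98.6 per arm it would be 1.21.

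**4. Power at 112, and at 12% loss** (224 × 0.88 = 197.1 analysed; 98.6 per arm, or 98-99 for binary endpoints), by the planned tests with the printed boundaries:

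| Endpoint | At 112 | After 12% loss |
|---|---|---|
| Mortality, 12% v 2%, Fisher | 80-81% | 73-74% |
| Composite, 14% v 3%, Fisher | 80-81% | 73-75% |
| INR above 1.5, 18% v 5%, unadjusted logistic | 86-89% | 80-84% |
| INR, 0.19, SD 0.5 | 80% | 75% |
| TEG G, 1.1, SD 3 | 77% | 72% |
| Base deficit, 2, SD 6.3 | 65% | 59% |
| Lactate, 1, SD 2 | 96% | 94% |

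The Fisher ranges span a single-look exact calculation at the final nominal level and a sequential simulation of 400,000 runs. The logistic ranges run from the Wald to the likelihood-ratio test. If only 2% are missing (110 per arm), mortality power is 79-80%.

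**5. Base deficit with no loss.**
- Required n = 2 × (2.836 × 6.3 / 2)² = 159.6 analysed per arm.
- Detectable difference at 112 = 2.836 × 6.3 × √(2/112) = 2.39. At 98.6 per arm it is about 2.55.
- Experimental-arm SD that would rescue the claim: √(112 × (2/2.836)² − 6.3²) = 4.0. An SD of 5 or 7 in that arm gives 74% or 60%.

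**The case against.** **Mortality may lose very little.** Section IV.H predicts under 2% missing vital status and counts unverified patients as alive. The 88 of 100 refers to an interim report that is not in these documents, and IV.H expects few missing laboratory values. This stands: the 12% case is conditional, especially for the primary endpoint.

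**Rounding.** After 12% loss, the mortality difference detectable at 80% by Fisher's test is about 10.4-10.5 points. The printed table itself needs 10.3-10.4 points, shown as 10. This also stands in part: at printed precision the mortality shortfall is small. It is clearer for INR (0.20 against 0.19) and TEG G (1.21 against 1.1).

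**The choice of test matters.** Under the table's continuity-corrected method, mortality at exactly 12% v 2% has 75-77% power at 112 and 69-70% at 99. INR above 1.5 has 80% and 74%. The figures above use the tests the protocol plans, which is the relevant basis. For mortality the loss from attrition is similar either way.

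**The look schedule.** IV.D.5 sets looks at 50, 100, 150 and 200. Equal spacing would put the last at 250, and 250 × 0.88 = 220, close to 224. But 250 is not printed, and the addendum states 224 as 74 above an enrolment of 150. The conflict in look timing is a separate matter.

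**The source of the 2 mEq/L.** The addendum's interim table shows base deficits of 11.2 and 9.2, which may be where 11 to 9 came from. That does not make the 80% claim true.

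**The plan admits low power.** Section IV.I.1 says a significant result is unlikely. That general remark does not correct the specific figures.

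**Conclusion.** Both parts hold. The 12% attrition is named but not applied: 112 is the analysed number that gives 80% and also half of the 224 to be enrolled. If 12% are in fact not analysed, attrition costs mortality, the composite, INR and TEG G about 5-7 points each, and the 80% claim fails for all four. It survives for lactate and, by logistic regression, for INR above 1.5. Keeping 112 analysed at that loss would take 112/0.88 = 127.3, or 128 enrolled per arm. The effect is modest, and for mortality it depends on an analysis set the documents leave unclear.

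The base-deficit error does not depend on attrition. With SD 6.3 in both arms, power is 65% at 112. Only an experimental-arm SD near 4.0, which the addendum does not state, would give 80%.

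This should be fixed because the extension rests on these figures.

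**What to change.** Keep 224 enrolled, the tests and the boundaries. At each of the eight places, do one of the following:

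- Delete the attrition parenthesis and say that the power assumes all 224 are analysed.
- Keep it and restate power, or the detectable difference, for about 197 analysed by the planned test: mortality 73-74%, composite 73-75%, INR 75%, INR above 1.5 80-84%, TEG G 72%, lactate 94%.

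In either case, correct base deficit. Give about 2.4 mEq/L as detectable at 112 per arm (about 2.5 after 12% loss), or 65% (59%) power for 2 mEq/L, and state the SD assumed in each arm.

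Add a sentence saying which randomized patients enter the mortality analysis. It should reconcile the 88 eligible of 100 enrolled with intent-to-treat (IV.D.3) and the follow-up of excluded patients (IV.H), and with unenrolment on transfer elsewhere (IV.J.9) and destruction of data on withdrawal (IV.M.1.d).

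The cost is addendum wording and less favourable printed figures.

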Sample sizes of 60 and 60 achieve 80% power to detect a difference of 0.25 between the group proportions at a significance level (alpha) of 0.050000 using a two-sided test. These results assume that 3 sequential tests are made using the O'Brien-Fleming spending function to determine the test boundaries.

Bound	aries (Bn	dry) for data l	ooks					
Details	when Sp	ending = O'Br	ien-Fleming,	N1 = 60, N2 =	=60, P1 = 0.25	P2 = 0.50		
		Lower	Upper	Nominal	Inc	Total	Inc	Total
Look	Time	Bndry	Bndry	Alpha	Alpha	Alpha	Power	Power
1	0.33	-3.71030	3.71030	0.000207	0.000207	0.000207	0.018650	0.018650
2	0.67	-2.51142	2.51142	0.012025	0.011890	0.012097	0.398801	0.417451
3	1.00	-1.99302	1.99302	0.046259	0.037903	0.050000	0.382549	0.800000
Details	when Sp	ending = O'Br	·ien-Fleming,	N1 = 68, N2 =	=68, P1 = 0.27	P2 = 0.50		
	-	Lower	Upper	Nominal	Inc	Total	Inc	Total
Look	Time	Bndry	Bndry	Alpha	Alpha	Alpha	Power	Power
1	0.33	-3.71030	3.71030	0.000207	0.000207	0.000207	0.018650	0.018650
2	0.67	-2.51142	2.51142	0.012025	0.011890	0.012097	0.398801	0.417451
3	1.00	-1.99302	1.99302	0.046259	0.037903	0.050000	0.382549	0.800000
Details	when Sp	ending = O'Br	·ien-Fleming,	N1 = 75, N2 =	=75, P1 = 0.28	P2 = 0.50		
	•	Lower	Upper	Nominal	Inc	Total	Inc	Total
Look	Time	Bndry	Bndry	Alpha	Alpha	Alpha	Power	Power
1	0.33	-3.71030	3.71030	0.000207	0.000207	0.000207	0.018650	0.018650
2	0.67	-2.51142	2.51142	0.012025	0.011890	0.012097	0.398801	0.417451
3	1.00	-1.99302	1.99302	0.046259	0.037903	0.050000	0.382549	0.800000

Addendum November 16, 2016

Based on the interim analyses, a proposed new sample size is: with 80% power, 95% confidence and assuming mean admission TEG G = 7 dynes/cm2 with standard deviation of 3 in the control group (based on the second interim analyses data), with 5 interim analyses (4 interim and 1 final, of which 3 already occurred), we will require 112 patients in each group (assuming the attrition rate observed in this RCT of 12%) to detect a difference of 1.1 dynes/cm2 (from 7 to 5.9 dynes/cm2) between the two mean TEG Gs. This results in a total of 224, which corresponds to an increase of 74 patients over the current sample size of 150 patients.

4. Secondary Objective 4: To determine if early administration of plasma in the field will improve the incidence of early postinjury acidosis compared to the current standard of care.

Secondary Endpoint 4: Admission acidosis. This is an endpoint for which there is ample evidence of a strong association of postinjury mortality and serious complications. ⁹¹⁻¹⁰⁰

a. Definition: Admission acidosis will be defined through base deficit (BD) or lactate levels upon ED arrival. The target time point is 30 minutes after ambulance arrival to injury scene. Our institution's average time from arrival of ambulance to scene till arrival in ED is 28 minutes. ⁸⁸ If both base deficit and lactate are obtained more than 60 minutes from arrival of ambulance to scene, they will not be used to define the endpoint.

- b. **Hypothesis 4.1:** Admission BD will be higher^{‡‡} among control patients compare to the experimental group patients.
- c. **Statistical test 4.1:** Linear regression will be used to compare the mean admission base deficit of the two groups. Statistical significance will be determined according to the interim analyses procedures describe below. If adjustment for pre-defined confounders is needed, we will use the above-defined method for continuous, normally distributed variables.
- d. **Interim analyses:** We planned 5 analyses (4 interim, 1 final), equally spaced, using the O'Brien-Fleming method to calculate two-sided boundaries, assuming a 95% confidence and 80% power.
- e. **Sample size and Power calculations:** This is a Phase 2 trial, powered to detect differences in this outcome as follows:

Power calculations: Admission Base Deficit

Assumptions 1: 80% power, 95% confidence, 2-tailed test, 3 equally spaced data analyses (2 interim, 1 final), using the O'Brien-Fleming method; control group mean admission BD=5.15 and standard deviation (SD) =5.1 (based on⁹²)

Power	N1	N2	Alpha	Beta	Mean 1	Mean 2	SD	Difference	Attrition Rate
0.800000	60	60	0.050000	0.200000	5.15	2.52	5.10	2.63	20%
0.800000	68	68	0.050000	0.200000	5.15	2.68	5.10	2.47	10%
0.800000	75	75	0.050000	0.200000	5.15	2.80	5.10	2.35	0

Sample sizes of 60 and 60 achieve 80% power to detect a difference of 2.63 between the two means, a clinically relevant difference, at a significance level (alpha) of 0.05 using a two-sided test. These results assume that 3 sequential tests are made using the O'Brien-Fleming spending function to determine the test boundaries.

Boundaries (Bndry) for data looks

	iury) ior uata i						
Details when S	pending = O'Br	ien-Fleming,	N1 = 60, N2 =	=60, S1 = 5.10,	S2 = 5.10, Di	ff = 2.63	
	Lower	Upper	Nominal	Inc	Total	Inc	Total
Look	Bndry	Bndry	Alpha	Alpha	Alpha	Power	Power
1	-3.71030	3.71030	0.000207	0.000207	0.000207	0.018650	0.018650
2	-2.51142	2.51142	0.012025	0.011890	0.012097	0.398801	0.417451
3	-1.99302	1.99302	0.046259	0.037903	0.050000	0.382549	0.800000
Details when S	pending = O'Br	·ien-Fleming,	N1 = 68, N2 =	=68, S1 = 5.10,	S2 = 5.10, Di	ff = 2.47	
	Lower	Upper	Nominal	Inc	Total	Inc	Total
Look	Bndry	Bndry	Alpha	Alpha	Alpha	Power	Power
1	-3.71030	3.71030	0.000207	0.000207	0.000207	0.018650	0.018650
2	-2.51142	2.51142	0.012025	0.011890	0.012097	0.398801	0.417451
3	-1.99302	1.99302	0.046259	0.037903	0.050000	0.382549	0.800000
Details when S	pending = O'Br	ien-Fleming,	N1 = 75, N2 =	=75, S1 = 5.10,	S2 = 5.10, Di	ff = 2.35	
	Lower	Upper	Nominal	Inc	Total	Inc	Total
Look	Bndry	Bndry	Alpha	Alpha	Alpha	Power	Power
1	-3.71030	3.71030	0.000207	0.000207	0.000207	0.018650	0.018650
2	-2.51142	2.51142	0.012025	0.011890	0.012097	0.398801	0.417451
3	-1.99302	1.99302	0.046259	0.037903	0.050000	0.382549	0.800000

^{‡‡} Although the hypothesis is worded as "higher", all tests will be two-tailed to control for differences in either direction (higher or lower than the other group).

Addendum November 16, 2016

Based on the interim analyses, a proposed new sample size is: with 80% power, 95% confidence and assuming mean admission BD = 11 mEq/L with standard deviation of 6.3 in the control group (based on the second interim analyses data), with 5 interim analyses (4 interim and 1 final, of which 3 already occurred), we will require 112 patients in each group (assuming the attrition rate observed in this RCT of 12%) to detect a difference of 2mEq/L (from 11 to 9mEq/L) between the two mean BDs. This results in a total of 224, which corresponds to an increase of 74 patients over the current sample size of 150 patients.

- f. Hypothesis 4.2: Admission lactate will be higher^{§§} among control patients compare to the experimental group patients. Statistical test 3.2: Linear regression will be used to compare the mean admission lactate of the two groups. Statistical significance will be determined according to the interim analyses procedures describe below. If adjustment for pre-defined confounders is needed, we will use the above-defined method for continuous, normally distributed variables.
- g. **Interim analyses:** We planned 5 analyses (4 interim, 1 final), equally spaced, using the O'Brien-Fleming method to calculate two-sided boundaries, assuming a 95% confidence and 80% power.
- h. **Sample size and Power calculations:** This is a Phase 2 trial, powered to detect differences in this outcome as follows:

Power calculations: Admission Lactate

Assumptions 1: 80% power, 95% confidence, 2-tailed test, 3 equally spaced data analyses (2 interim, 1 final), using the O'Brien-Fleming method; control group mean admission lactate=2.0 mmol/L and standard deviation (SD) =2.0 (based on $^{67, 81, 91}$)

		(-)		- /					
Power	N1	N2	Alpha	Beta	Mean 1	Mean 2	SD	Difference	Attrition Rate
0.800000	60	60	0.050000	0.200000	2.00	0.97	2.00	1.03	20%
0.800000	68	68	0.050000	0.200000	2.00	1.03	2.00	0.97	10%
0.800000	75	75	0.050000	0.200000	2.00	1.08	2.00	0.92	0

Sample sizes of 60 and 60 achieve 80% power to detect a difference of 1.03 mmol/L between the two means, a clinically relevant difference, at a significance level (alpha) of 0.05 using a two-sided test. These results assume that 3 sequential tests are made using the O'Brien-Fleming spending function to determine the test boundaries.

Boundaries (Bndry) for data looks

Details when	n Spending = O'Bi	ien-Fleming,	N1 = 60, N2 =	=60, S1 = 2.00,	S2 = 2.00, Di	ff = 1.03	
	Lower	Upper	Nominal	Inc	Total	Inc	Total
Look	Bndry	Bndry	Alpha	Alpha	Alpha	Power	Power
1	-3.71030	3.71030	0.000207	0.000207	0.000207	0.018650	0.018650
2	-2.51142	2.51142	0.012025	0.011890	0.012097	0.398801	0.417451
3	-1.99302	1.99302	0.046259	0.037903	0.050000	0.382549	0.800000

Details when Spending = O'Brien-Fleming, N1 = 68, N2 = 68, S1 = 2.00, S2 = 2.00, Diff = 0.97

^{§§} Although the hypothesis is worded as "higher", all tests will be two-tailed to control for differences in either direction (higher or lower than the other group).

	Lower	Upper	Nominal	Inc	Total	Inc	Total
Look	Bndry	Bndry	Alpha	Alpha	Alpha	Power	Power
1	-3.71030	3.71030	0.000207	0.000207	0.000207	0.018650	0.018650
2	-2.51142	2.51142	0.012025	0.011890	0.012097	0.398801	0.417451
3	-1.99302	1.99302	0.046259	0.037903	0.050000	0.382549	0.800000
	T	II	NT 1	=75, S1 = 2.00,	T. 4.1		T.4.1
Look	Lower	Upper	Nominal	Inc	Total	Inc	Total Bower
Look	Bndry	Bndry	Alpha	Inc Alpha	Alpha	Inc Power	Power
Look 1		11		Inc		Inc	
Look 1 2	Bndry	Bndry	Alpha	Inc Alpha	Alpha	Inc Power	Power

Addendum November 16, 2016

Based on the interim analyses, a proposed new sample size is: with 80% power, 95% confidence and assuming mean admission lactate=5 mg/dL with standard deviation of 2 in the control group (based on the second interim analyses data), with 5 interim analyses (4 interim and 1 final, of which 3 already occurred), we will require 112 patients in each group (assuming the attrition rate observed in this RCT of 12%) to detect a difference of 1 mg/dL between the two mean lactates. This results in a total of 224, which corresponds to an increase of 74 patients over the current sample size of 150 patients.

G. Exploratory analyses

- Exploratory analysis 1: 24-hour mortality Based on the control arm of the recent ROC trial⁶⁷ and our trauma registry data, the control group 24-hours mortality is estimated to be between 19% and 26%.
 - a. **Definition:** 24-hours mortality is defined as death within 24 hours post injury (death of any cause). Research coordinators will verify the vital status of all patients 24 hours postinjury and determine the time of death in relationship to injury.
 - b. **Hypothesis:** 24-hour mortality will be significantly higher^{***} in control patients compared to experimental group patients.
 - c. Statistical test: Logistic regression will be used to compare the 24-hour mortality in the two groups. Statistical significance will be evaluated at each interim analyses for the primary outcomes and p-values, as well as 95% and 99% confidence intervals will be reported to the DSMB for analyses. If adjustment for pre-defined confounders is needed, we will use the above-defined method for categorical, binary variables. Time from injury to death will be evaluated using the Kaplan Meyer curves, which will be compared using SAS PROC LIFETEST. We will use the Wilcoxon test (which places more weight on shorter survival times) and the log-rank test (which privileges longer survival times). SAS PROC LIFETEST also constructs statistics to test for

^{***} Although the hypothesis is worded as "lower", all tests will be two-tailed to control for differences in either direction (higher or lower than the other group).

association between covariates and the lifetime variable through rank tests for the association of survival time with covariates, if there are potential confounders detected using the above-described procedures.

2. Pre-planned subgroup analyses:

- a. **Blunt trauma mechanism:** There is evidence to suggest that the coagulation and inflammatory responses to injury differ by trauma mechanism, as they cause different tissue damage.^{101, 102}
 - 1. **Hypothesis:** Blunt trauma patients will have different effect sizes than penetrating trauma victims regarding the primary endpoint and secondary endpoints
 - 2. **Statistical tests:** Same tests described for primary and secondary endpoints stratified by mechanism of injury (blunt vs. penetrating). We will compare the 95% confidence intervals to determine overlap between the blunt and penetrating groups for each endpoint.
- b. Absence vs. presence of serious traumatic brain injury (TBI): there is evidence to suggest a differential coagulation and inflammatory response by the presence of TBI.^{101, 103, 104}
 - Hypothesis: Patients with associated TBI (defined as Abbreviated Injury Score, AIS, for Head >3) will have different effect sizes than their counterparts without TBI regarding the primary endpoint and secondary endpoints.
 - Statistical tests: Same tests described for primary and secondary endpoints stratified by presence of TBI. We will compare the 95% confidence intervals to determine overlap between the two groups for each endpoint.
- c. Presence of very severe hemorrhagic shock (HS, defined as SBP≤70 mmHg) versus severe HS (defined as SBP 71-90mmHg + Heart rate>=108bpm): There is evidence that the patients with very severe HS shock are more likely to require massive transfusion and present severe coagulopathy, thus potentially having differential mortality.¹⁰⁵
 - Hypothesis: Patients with very severe hemorrhagic shock (defined as SBP≤70mmHg) will have different effect sizes than their counterparts with severe hemorrhagic shock (defined as SBP 71-90mmHg +heart rate>=108bpm) regarding the primary endpoint and secondary endpoints.
 - Statistical tests: Same tests described for primary and secondary endpoints stratified by degree of hemorrhagic shock. We will compare the 95% confidence intervals to determine overlap between the two groups for each endpoint. Overall experiment error will be adjusted for the number of subgroups being analyzed using the Bonferroni method.

- **3.** Adverse-outcome free days: There is ample evidence suggesting a strong association with these outcomes and mortality. These outcomes were devised by the ARDS Net group to overcome survivor bias, initially for mechanical ventilation and quickly expanded to include other outcomes potentially biased by survivorship. Outcome-free-days (OFD) as proposed by the NIH sponsored ARDSnet trials,¹⁰⁶ takes the observation time into account. We apologize for not providing more information on this measure; we assumed the reviewers were familiar with it as it is so often used in recent clinical trials. Indeed, ALI-free days, MOF-free days and ventilator-free days (VFD) were proposed exactly to deal with the survivor –bias stated by the reviewers.
 - a. Definition: VFDs can be arbitrarily defined as the number of days between successful weaning from mechanical ventilation and day 28 after study enrollment. The 28-day landmark was suggested both because interventional trials in acute lung injury typically involve a 28day treatment/follow-up period after the patient enrolls in the trial and because most, but not all, patients with acute lung injury have either died or been successfully weaned from mechanical ventilation by day 28. VFDs are defined as follows:

VFDs = 0: If the patient dies before 28 days.

VFDs = (28 - x): If the patient is successfully weaned from mechanical ventilation within 28 days, where x is the number of days spent receiving mechanical ventilation.

VFDs = 0: If the patient requires mechanical ventilation for 28 days or more.

For example, VFD=2 means that the patient spent at least 26 days on the ventilator or, less likely, died within 2 days without being on a ventilator, both of which are considered poor outcomes.

- b. We will assess two adverse-outcome-free days measured over 28 days, as follows:
 - 1. Ventilation free days
 - 2. Acute Lung Injury (ALI) free days (as defined by the validated Denver Lung Dysfunction score)
- c. **Hypothesis:** Experimental group patients will have longer ⁺⁺⁺adverseoutcome-free-days than control patients.
- d. **Statistical test:** these outcomes are often skewed and non-normally distributed. Log transformation has been shown to be a good alternative to approximate normality for them. Thus, we will utilize linear regression to examine differences between the two groups. If adjustment for covariates is needed, we will proceed with the method for continuous normally distributed variables. In the case, normality cannot be achieved (as determined by the Shapiro-Wilk test for

^{†††} Although the hypothesis is worded as longer, the tests will be two-tailed to examine association in either direction.

normality), and there is no need to adjust for confounders, we will report median and interquartile ranges as measures of data central tendency and dispersion and use the Wilcoxon test to evaluate differences. If adjustment for covariates is needed, then we will resort to categorization of the outcomes, based on previously established, clinically meaningful cutoffs.⁸⁰ Overall experiment error will be adjusted for the number of adverse-outcomes-free-days parameters being analyzed using the Bonferroni method.

4. Temporal trends:

a. Coagulation Profile: We will assess temporal trends from pre-hospital coagulation variables (as described below) at 2, 4, 6, 12, 24, 72 hours and 28 days post-injury. The proposed coagulation measurements will also test the efficacy of plasma first resuscitation, since plasma is primarily employed for restoring levels of Factors II, V, VII, X and possibly XIII with a goal of greater than 20%, which is known to be effective for the cessation of surgical bleeding¹⁰⁷. In addition, there are major changes in the post-shock plasma affecting levels of proteins involved in regulating proteolysis, membrane lipid binding and stabilizing potentially cytotoxic intracellular components released after tissue injury.

